9.1.7 Adverse Events

Information regarding occurrence of adverse events will be captured throughout the study. Duration (start and stop dates and times), severity/grade, expectedness, outcome, treatment and relation to study drug will be recorded on the case report form (CRF). Please refer to section 11 “Adverse experience reporting and documentation” for more details.

We will further protect subjects from unanticipated risks by monitoring for adverse effects at every visit during treatment by carefully checking for any adverse reactions and by assessing suicidality with the CSSRS (Posner et al., 2007). The careful monitoring of suicidal ideation and behavior is a critical component of any study conducted in patients with depressive disorder and treatment emergent suicidal ideation has been associated with the use of antidepressants and other drugs with CNS penetration. A study clinician assesses SI, suicidal behavior and risk at each study visit and a CSSRS is completed.

If, at any point during the clinical trial, a participant will be assessed by the study physician with a suicidal ideation with any intent or plan, as measured by a C-SSRS score of greater than 3 during the past week and with either a GCI-S score ≥ 6 (indicating extreme illness severity) or a CGI-I score ≥ 6 (indicating an extreme worseness of the symptoms), the site PI, or his designee, will conduct a safety review to determine the appropriate course of action including whether acute intervention is needed and whether it is in the best interests of the subject to continue in the study. For more details regarding the safety review procedures, please refer to section 5.3 “Safety evaluation”.

9.2 Clinical Laboratory Measurements

9.2.1 Hematology and Blood Chemistry Profile

Blood will be obtained and sent to each site’s clinical hematology lab for a complete blood count with differential, Hemoglobin, Hematocrit, Electrolytes, Metabolic Panel, Lipid Panel, Thyroid Function Tests, Hepatic and Renal Function Tests, Serology (only at screening) and plasmatic drug concentrations. Blood samples for determination of plasmatic ezogabine concentrations will be collected at the Primary outcome visit (V5), stored at each site (at MSSM blood sample will be stored at [name], Mount Sinai School of Medicine, 1425

[name]) and will be processed at a specialized lab during the course of the study. These samples will be handled, processed, and mailed in accordance with applicable state, federal, and international regulations.

Please, refer to table 2 “Schedule of Assessments, Outcome Measures, Labs, and Procedures.”

9.2.2 Pregnancy Test

A urine pregnancy test will be obtained from female subjects who are of childbearing age prior to their participation in the study (screening visit, V-1), at baseline (V0), at the primary outcome visit (V5), and at study end (V6).

9.2.3 Urinalysis

Urine will be obtained and each site’s clinical laboratory for determination of color, urine special gravity, osmolality, cellules, proteins and bacteria prior to their participation in the study (screening visit; V-1) and at study exit (V6). A urine toxicology screen for drugs of abuse will be performed at screening (V-1), baseline (V0), primary outcome visit (V5) and study exit (V6).

9.3 Pharmacokinetics Measurements

Venous blood samples will be collected for determination of plasmatic ezogabine concentrations at the time point specified in Table 2 and will be summarized by visit. Blood samples will be stored at each site and will be processed at a specialized lab throughout the course of the study. Results will be sent to the study data manager (unblinded member of the Mount Sinai study team) via the lab website’s secure online account portal.

10 EVALUATIONS BY VISIT

Study visits may occur within 3 days before or after the scheduled visit, except for V5 (Primary outcome visit), which may occur at any point after participants have been on their highest tolerated treatment dose from at least one week (7 days) up to a maximum of two weeks (14 days), and V8 which may take place within six weeks of the Primary Outcome Visit (V5). Please refer to Table 2 “Schedule of Assessments, Outcome Measures, Labs, and Procedures.”

10.1 Screening Visit (Visit -1)

1. Review the study with the subject and obtain written informed consent and HIPAA authorization.
2. Review inclusion and exclusion criteria.
3. Assign the subject a unique screening number.
4. Record demographics data.
 - Demographics Form
 - Edinburg Handedness Inventory

5. Perform a clinical interview.
6. Record medical, psychiatric, medication and treatment history, diagnosis date, and prior treatments.
 - Medical History Form
 - Family Psychiatric History Form
 - Anti-Depressant Treatment History Form
7. Record concomitant medications and tapering of prohibited medications (if applicable).
8. Perform a complete physical examination.
9. Perform and record vital signs and EKG.
10. Perform an ophthalmological exam.
11. Collect blood for clinical laboratory tests (complete blood count with differential, Hemoglobin, Hematocrit, Electrolytes, Metabolic Panel, Lipid Panel, Thyroid Function Tests, Hepatic and Renal Function Tests, and serology) and urine for urinalysis, urine toxicology and pregnancy test (female subjects who are of childbearing age).
12. Perform self and clinician administered ratings scale:
 - SCID-5-RV
 - SHAPS
 - CGI-S
 - CSSRS
 - MMSE
13. Schedule subject for Visit 0 within 6 weeks.

Note: The screening visit may occur on up to three separate days. The whole procedures will be completed before the randomization day (baseline visit - visit 0) and within six weeks of the first screening visit. Screening measures may be completed under a separate screening protocol at each site. As long as the assessments are completed within four weeks of the signing of consent for this protocol, the screening measures will not be repeated.

10.2 Baseline (Visit 0)

1. Obtain interval medical history.
2. Record any AEs.
3. Record changes to concomitant medications.
4. Collect urine for toxicology and pregnancy test (female subjects who are of childbearing age)
5. Randomization of the subject.
6. Illustrate drug administration and patient diary compilation.
7. Perform self and clinician administered ratings scale:
 - SHAPS
 - TEPS
 - ACIPS
 - SLIPS

- QIDS-SR
- MASQ
- MADRS
- CSSRS
- CGI-S
- CGI-I
- WHODAS
- PRT
- Structural MRI, fMRI during IFT, resting state connectivity.

Note: The Baseline/Randomization Visit should take place within six-weeks of the date that the subject signed consent for this study.

10.3 Double Blind Treatment Period (Visits 1 – 4)

1. Obtain interval medical history.
2. Record any AEs and review subject diary for adverse experiences and dosing compliance.
3. Record changes to concomitant medications.
4. EKG*
5. Perform self and clinician administered ratings scale:
 - SHAPS
 - TEPS
 - ACIPS
 - SLIPS
 - QIDS-SR
 - MADRS
 - CSSRS
 - CGI-S
 - CGI-I

Note: Study Visits 1, 2, 3, and 4 are due to take place 1, 2, 3, and 4 weeks after the Baseline/Randomization Visit (Visit 0) respectively. To allow for scheduling feasibility, Visits 1-4 can take place within 3 days before or after the scheduled visit.

** During the Double Blind Treatment Period (Visits 1 – 4), EKG will occur only on visit 4, when participants reach drug exposure of 750 mg daily over the prior week and are poised to escalate to the highest dose tested in the study of 900 mg daily. The additional EKG screening at visit 4 will ensure that no adverse QT effects have emerged prior to escalating to the highest dose. If a subject will show a QT intervals over 500 milliseconds or a 60-milliseconds increase in the QT interval from baseline, the dose will not be escalated and the subject will be tapered down from study medication over a three-week period. The study participant will be asked to return to study site to complete the primary outcome*

assessment after one week and will be exited from study upon completion of the taper period. Please, refer to section 10.6 Study exit Visit (Visit) and early withdrawal.

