2.1 Risk / Benefit Assessment

The most common adverse effects of ezogabine are dizziness (23%), drowsiness (22%) and fatigue (15%). No contraindications to treatment were reported in the manufacturer’s label. Since QT prolongation has been observed, ECG will be monitored at screening and study exit. Skin discoloration around the lips or nail bed, either blue or gray, has been reported and is estimated to affect up to 10% of patients treated for more than two years. Below we summarize the risks of the study drug and strategies to mitigate risk. In addition, please see section 5.3 “Safety Evaluation” for additional description of study safety evaluations.

QT Prolongation:

QT prolongation has been observed in healthy subjects during a randomized, double-blind study where the maximum mean increase of QT interval of 7.7 msec was observed at 3 hours after 22 days of treatment with ezogabine 1,200 mg daily. No effects on heart rate, PR, or QRS intervals were noted. In our trial, the dosage of 1200 mg daily will not be reached and participants will be at the highest dose of 900 mg per day, respectively, for one week. Moreover, since patients who are prescribed ezogabine with medicines known to increase QT interval or who have known prolonged QT interval, congestive heart failure, ventricular hypertrophy, hypokalemia, or hypomagnesemia should be observed closely, to ensure participants’ safety we will exclude from the trial subjects with:

- unstable medical illness including ischemic heart disease or other cardiovascular disease;
- history of QT prolongation or congenital QT syndrome
- prolonged QT interval at screening (QTc > 480 msec)
- clinically significant abnormalities of laboratory tests and EKG

To reduce risks for participants in this trial, an EKG will be performed at the screening, at visit 4 (to monitor any QT effects that have emerged prior to escalating to the highest dose; see Section 10.3 “Double Blind Treatment Period” for additional details) and at study exit visits.

Skin Discoloration:

Skin discoloration around the lips or nail bed, either blue or gray, has been reported and is estimated to affect up to 10% of patients treated for more than two years. Given the limited exposure to the study drug in the current study, we anticipate the risk of skin discoloration to study participants will be very small.

Suicidality:

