10.4 Primary outcome visit (Visit 5)

1. Obtain interval medical history.
2. Record any AEs and changes in concomitant medications and review subject diary for adverse experiences and dosing compliance.
3. Collect urine for toxicology and pregnancy test (female subjects who are of childbearing age)
4. Illustrate drug tapering schedule.
5. Perform self and clinician administered ratings scale:
 - SHAPS
 - TEPS
 - ACIPS
 - SLIPS
 - QIDS-SR
 - MASQ
 - MADRS
 - CSSRS
 - CGI-S
 - CGI-I
 - WHODAS

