10.5 Taper Period (Phone calls* 1-2)

1. Perform a brief interview and history interval.
2. Complete the phone check-in form.

3. Record any new medical problems and general tolerability.
4. Record changes to concomitant medications and review dosing compliance.
5. Provide information on the next dose of the drug, according to the tapering schedule.

The taper period will occur over a three-week period according to the following scheme:

Study drug (ezogabine)
750 mg orally daily for 1 week
600 mg orally daily for 1 week
300 mg orally daily for 1 week
Discontinue

Subjects who are not able to tolerate the 900mg daily dose will follow one of the below taper schedules depending on the maximally tolerable dose.

Case 1. Patient is taking 750 mg/daily at primary outcome visit: 2-week taper

Study drug (ezogabine) – 750 mg
600 mg orally daily for 1 week
300 mg orally daily for 1 week
Discontinue

In Case 1, subjects will be contacted by a research coordinator for Visits 6 and 7 during the first and second weeks of the taper period, respectively.

Case 2. Patient is taking 600 mg/daily at primary outcome visit: 1-week taper

Study drug (ezogabine) – 600 mg
300 mg orally daily for 1 week
Discontinue

In Case 2, subjects will be contacted by a research coordinator for Visit 6 during the first week of the taper period. The Visit 7 telephone call will not take place as the Study Exit Visit will be scheduled after the subject completes their first week of the medication taper.

Case 3. Patient is taking 450 mg/daily at primary outcome visit: 1-week taper

Study drug (ezogabine) – 450 mg
300 mg orally daily for 1 week
Discontinue

In Case 3, subjects will be contacted by a research coordinator for Visit 6 during the first week of the taper period. The Visit 7 telephone call will not take place as the Study Exit Visit will be scheduled after the subject completes their first week of the medication taper

Case 4. Patient is taking 300 mg/daily at primary outcome visit: No additional taper needed

In Case 4, subjects who are taking a maximum daily dose of 300mg will not require further taper before ending study drug intake. In these cases, subjects will not undergo a taper period and/or complete a Visit 6 or Visit 7 telephone call. The study exit visit will be scheduled after completion of the the Primary Outcome Visit (V5).

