10.6 Study exit Visit (Visit 6) and early withdrawal

1. Perform a clinical interview and history interval
2. Record any AEs.
3. Record changes to concomitant medications and review subject diary for adverse experiences and dosing compliance.
4. Perform a physical examination with recording of vital signs
5. Perform EKG.
6. Perform an ophthalmological exam.
7. Collect blood for clinical laboratory tests
8. Collect urine for urinalysis, urine toxicology and pregnancy test (applies to women of child-bearing potential only).
9. Perform self and clinician administered ratings scale:
 - SHAPS
 - TEPS

- ACIPS
- SLIPS
- QIDS-SR
- MADRS
- CSSRS
- CGI-S
- CGI-I

10. PRT*.

11. Structural MRI, fMRI during IFT, resting state connectivity*

Note: The exit visit may occur on up to three separate days, within 6 weeks of the Primary Outcome Visit (Visit 5). The subject will be considered exited from the study when all the procedures listed above will be completed.

** This procedure will be performed ONLY for early withdrawal visits that take place before completion of the primary outcome visit. Capturing outcome data for patients who do not complete the full study protocol will allow a more precise estimate of the treatment effect.*

Provision of study follow-up for treatment emergent adverse events at study exit: in case of any adverse event (including, but not limited to suicidal ideation or behavior) present at the study exit visit, subject will be referred to follow-up care until the event is resolved and/or a stable care plan is in place. The site PI will follow up with the subject until the abnormal parameter or symptom has resolved or stabilized.

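### The V4 stop rule in Protocol 10.3 is worded as uncorrected QT while eligibility uses QTc, with no formula named; the ECG mark in Table 2 should also be checked against V4

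*Protocol*

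**What the plan says.** **The check.** Protocol 10.3 places one ECG within Visits 1 to 4, at V4, after a week at 750 mg/day. Its purpose is explicit: "The additional EKG screening at visit 4 will ensure that no adverse QT effects have emerged prior to escalating to the highest dose". The risk-reduction sentence in Protocol 2.1 agrees. It lists ECGs at screening, at study exit and "at visit 4 (to monitor any QT effects that have emerged prior to escalating to the highest dose".

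**The stop rule.** The trigger in 10.3 is "QT intervals over 500 milliseconds or a 60-milliseconds increase in the QT interval from baseline". If it is met, the dose is not raised, the patient is tapered over three weeks, returns after one week for the primary outcome assessment, and leaves the study when the taper ends.

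**Eligibility.** Protocol 2.1 and exclusion 12 in 6.3 both exclude a QTc above 480 ms at screening. Neither they nor 10.3 name a correction formula.

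**The schedule.** In the extracted text of Protocol Table 2, the ECG row has three marks. They fall in the columns for screening, V5 and exit, and the V4 column is blank. The V5 procedure list in 10.4 contains no ECG.

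**The concern.** The rule in 10.3 is mandatory: it ends escalation and takes the patient off drug. Two sites should not be able to apply it differently. Raw QT shortens as heart rate rises, so a fixed limit on raw QT is a different test at each heart rate. Patients are admitted on one scale and stopped on another. The 60 ms limb also refers to a baseline that the rule does not define.

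Table 2 matters because sections 9 and 10 send the reader there for the schedule. If the printed table does mark V5 and not V4, a site booking from it could miss the on-drug ECG required before 900 mg. An ECG at V5 comes after 7 to 14 days on the highest tolerated dose, which is too late to decide whether to escalate.

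**Working it through.** **1. The dose sequence (reproduces the plan's figure).** Section 8.4.1 starts at 300 mg/day and adds 150 mg/day each week: 300, 450, 600, 750, 900 in weeks 1 to 5. V4 therefore ends the 750 mg week, as 10.3 says.

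**2. What the literal rule means as QTc.** The documents give no heart rates and no formula, so both are assumptions here. With HR in beats/min:

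- Bazett: QTc = QT × (HR/60)^(1/2)
- Fridericia: QTc = QT × (HR/60)^(1/3)

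| HR (assumed) | QTc when QT = 500 ms, Bazett / Fridericia | QTc change when QT rises 60 ms at constant HR |
|---|---|---|
| 50 | 456 / 471 | 54.8 / 56.5 |
| 60 | 500 / 500 | 60 / 60 |
| 70 | 540 / 526 | 64.8 / 63.2 |
| 80 | 577 / 550 | 69.3 / 66.0 |
| 90 | 612 / 572 | 73.5 / 68.7 |

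At 70 to 80 beats/min the literal 500 ms limb is 26 ms (526 − 500) to 77 ms (577 − 500) looser than QTc 500. Below 60 beats/min it is stricter.

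**3. Slow heart rates.** A patient at the permitted QTc of 480 ms has a raw QT of 500 ms when (HR/60) raised to the formula's power equals 480/500 = 0.96:

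- Bazett: HR = 60 × 0.96² = 55.3
- Fridericia: HR = 60 × 0.96³ = 53.1

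Below these rates such a patient meets the stop rule with no change in QTc. Assignment is blinded, so this could happen in either arm.

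**4. The 60 ms limb.** At constant heart rate it barely differs from a QTc rule (last column). It misses a larger rise only if the rate also changes. For example, take QTc going from 450 to 520 ms while HR goes from 70 to 80:

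- Bazett: raw QT goes from 416.6 to 450.3, a rise of 33.7 ms
- Fridericia: raw QT goes from 427.5 to 472.5, a rise of 45.0 ms

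A 70 ms rise in QTc would then not trigger a raw-QT limit of 60 ms.

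**5. Which ECG is baseline.** The V0 list in 10.2 has no ECG and Table 2 shows none at V0. The screening ECG is the only scheduled pre-dose ECG, so it must serve as baseline.

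**6. Table 2 columns.** The ten columns are V-1 and V0 to V8; the exit visit is V8 in the table and V6 in much of the text. Counting extracted cells puts the ECG marks in columns 1, 7 and 10. The toxicology row has marks in 1, 2, 7 and 10, and 9.2.3 says that test is "performed at screening (V-1), baseline (V0), primary outcome visit (V5) and study exit (V6"), so column 7 is V5. The pregnancy-test, serum-level and neuroimaging rows agree. The visit-label row is broken in extraction, however, so a one-cell shift of this single mark cannot be excluded.

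**The case against.** The best defence of 10.3 is the protocol's own usage. Both places that set an eligibility limit speak of a prolonged QT interval and then define it as QTc, so a reader could fairly take 10.3 the same way. That stands as the probable intention, but the stop rule does not say so and no formula is given anywhere. It is also fair that few patients should come near either limb: 2.1 reports a maximum mean QT increase of 7.7 ms at 1,200 mg/day, above this trial's dose, and no heart-rate effect. The example with a changing heart rate is therefore unlikely to be common. Other safeguards exist too. Section 6.3 excludes patients with a QT history or on QT-prolonging drugs, and 8.4.1 lets the investigator hold the dose for a suspected dose-dependent effect.

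On the schedule, a reader might infer several stronger things that the documents do not support:

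- **That the V4 check is absent or firmly contradicted.** Sections 2.1 and 10.3 require it without ambiguity, and the Table 2 evidence is one cell in a table with a broken header. The row has three marks and 2.1 names three ECGs, so one mark placed a visit late, by typing or by extraction, is a simple explanation.
- **That a site using Table 2 would have no ECG before 900 mg.** The screening ECG is marked. What could be missed is the on-drug ECG.
- **That the opening of 2.1 sets a competing schedule.** Its statement that "ECG will be monitored at screening and study exit" does not exclude other visits. The same section adds V4, and 10.3 calls that ECG additional.
- **That an ECG on 900 mg is required.** With ECGs at screening, V4 and exit, none is scheduled on 900 mg, because the exit ECG follows a taper of three weeks from that dose. The text of 2.1 sets exactly those three visits, so a V5 ECG is the sponsor's choice.

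**Conclusion.** The wording point holds. The stop rule in 10.3 is stated as raw QT while eligibility is stated as QTc, and no correction formula is named. Read literally, the 500 ms limb is looser than QTc 500 above 60 beats/min (by 26 to 77 ms at 70 to 80 beats/min) and stricter below. It could taper an unaffected patient who entered at QTc 480 ms with a heart rate under about 53 to 55. These sizes rest on assumed heart rates and on Bazett and Fridericia as the candidate formulas. The 60 ms limb is little affected unless heart rate changes. The practical effect should be small, because large QT changes are not expected at this dose.

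The Table 2 point is probable but not firm. If the printed page also shows V5 and not V4, it concerns at most the 24 patients assigned to ezogabine who would step to 900 mg, and only at a site that follows the table rather than 10.3.

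Neither point affects the endpoints, power or alpha. The rule is a mandatory safety threshold and the correction costs almost nothing, so it should be made.

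**What to change.** 1. Reword the rule in 10.3 as QTc above 500 ms, or a QTc increase of 60 ms from the screening ECG. Name one correction formula and use it in both 6.3 and 10.3.
2. Check the ECG row of Table 2 on the original page. If V4 is blank there, mark V4 so that the table agrees with 2.1 and 10.3.
3. If the V5 mark is genuine, decide whether an ECG on 900 mg is wanted. If so, keep the mark and add ECG to the 10.4 list; if not, remove it. This is at the sponsor's discretion.

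The cost is one sentence in 10.3, a formula name in 6.3 and possibly one table mark. The V4 ECG is already required, so it adds no procedure. Keeping a V5 ECG would add one recording per patient at an existing visit.

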10.4 Primary outcome visit (Visit 5)

1. Obtain interval medical history.
2. Record any AEs and changes in concomitant medications and review subject diary for adverse experiences and dosing compliance.
3. Collect urine for toxicology and pregnancy test (female subjects who are of childbearing age)
4. Illustrate drug tapering schedule.
5. Perform self and clinician administered ratings scale:
 - SHAPS
 - TEPS
 - ACIPS
 - SLIPS
 - QIDS-SR
 - MASQ
 - MADRS
 - CSSRS
 - CGI-S
 - CGI-I
 - WHODAS
6. PRT
7. Structural MRI, fMRI during Incentive Flanker Task (IFT), resting state connectivity.
8. Beginning of the tapering period, according to FDA guidelines.

Note: The Primary Outcome (Visit 5) study visit will be performed when participants are on the highest tolerated treatment dose from at least one week (7 days) up to a maximum of two weeks (14 days). During this time, subjects will remain on the same dose of study medication (i.e. the highest tolerate dose) and the taper will not be initiated until the Primary Outcome Visit has been completed.

At the discretion of the investigator, the study team can repeat any and all primary outcome procedures on an alternate date (within the given V5 study window of + 7-14 days) if the visit is unable to completed as originally scheduled (e.g., due to fMRI scanner malfunction, due to subject and/or study team availability, etc.) given that the procedures are not clinically contraindicated.

